## APPENDIX 3. EQ-5D-5L INDEX VALUE CALCULATION

EQ-5D-5L health states, defined by the EQ-5D-5L descriptive system, may be converted into a single index value using an appropriate EQ-5D-5L value set. If a standard EQ-5D-5L value set is not available, but an EQ-5D-3L value set is available, a “crosswalk” value set can be used to derive the index value. For multiregional trials, EuroQol recommends applying a single standard value set (or crosswalk value set) to all study sites. For this study, the US EQ-5D-5L standard value set will be used for all countries.

Please refer the following EuroQol website for EQ-5D-5L value sets and further information.

<https://euroqol.org/publications/key-euroqol-references/value-sets/>

**APPENDIX 4. INTERNATIONALLY AGREED ORDER FOR SYSTEM ORGAN CLASS**

Internationally Agreed Order
Infections and infestations
Neoplasms benign, malignant and unspecified (incl cysts and polyps)
Blood and lymphatic system disorders
Immune system disorders
Endocrine disorders
Metabolism and nutrition disorders
Psychiatric disorders
Nervous system disorders
Eye disorders
Ear and labyrinth disorders
Cardiac disorders
Vascular disorders
Respiratory, thoracic and mediastinal disorders
Gastrointestinal disorders
Hepatobiliary disorders
Skin and subcutaneous tissue disorders
Musculoskeletal and connective tissue disorders
Renal and urinary disorders
Pregnancy, puerperium and perinatal conditions
Reproductive system and breast disorders
Congenital, familial and genetic disorders
General disorders and administration site conditions
Investigations
Injury, poisoning and procedural complications
Surgical and medical procedures
Social circumstances
Product issues

## APPENDIX 5. ADVERSE EVENT OF SPECIAL INTEREST (AESI)

During the trial ongoing period and prior to database lock, adverse event customized query defined in this section is used more for AESI reconciliation purposes. Electronic data capture (EDC) system of clinical database contains an AESI tick box, which allow any event term listed below be ticked, thus would encompass any such event in EDC. In that way AESI per customized query (such as hyperprolactinemia-related adverse event) can be reconciled for any terms that potentially meet the protocol AESI criteria which have not been identified as such via the AESI tick box (and vice versa). Final definition of each customized query will be finalized right before the DBL and displayed in this SAP before the sign-off. AE preferred terms listed in this section are per MEDDRA version 24.1.

### A5.1 Hyperprolactinemia-related AEs (Customized)

"Hyperprolactinemia-related AEs" (customized) is defined as AEs with any of the following preferred terms and all preferred terms that include the word "FRACTURE".

Hyperprolactinemia		
AMENORRHOEA	AMENORRHOEA-GALACTORRHOEA SYNDROME	ANORGASMIA
ANOVULATORY CYCLE	BLOOD OESTROGEN ABNORMAL	BLOOD OESTROGEN DECREASED
BLOOD PROLACTIN ABNORMAL	BLOOD PROLACTIN INCREASED	BONE DEMINERALISATION
BONE DENSITY ABNORMAL	BONE FORMATION TEST ABNORMAL	BONE METABOLISM BIOCHEMICAL MARKER INCREASED
BONE METABOLISM DISORDER	BONE RESORPTION TEST ABNORMAL	BREAST DISCHARGE
BREAST DISCOMFORT	BREAST DISORDER	BREAST DISORDER FEMALE
BREAST DISORDER MALE	BREAST ENGORGEMENT	BREAST ENLARGEMENT
BREAST FIBROSIS	BREAST HYPERPLASIA	BREAST INFLAMMATION
BREAST OEDEMA	BREAST PAIN	BREAST SWELLING
BREAST TENDERNESS	DISTURBANCE IN SEXUAL AROUSAL	EJACULATION DISORDER
ERECTILE DYSFUNCTION	FEMALE ORGASMIC DISORDER	FEMALE SEXUAL AROUSAL DISORDER
FEMALE SEXUAL DYSFUNCTION	FIBROCYSTIC BREAST DISEASE	GALACTOCELE
GALACTORRHOEA	GALACTOSTASIS	GYNAECOMASTIA
HIRSUTISM	HYPERPROLACTINAEMIA	HYPOGONADISM
HYPOMENORRHOEA	INFERTILITY	LIBIDO DECREASED
LIBIDO DISORDER	MACROPROLACTINAEMIA	MALE ORGASMIC DISORDER
MALE SEXUAL DYSFUNCTION	MENSTRUAL DISORDER	MENSTRUATION DELAYED
MENSTRUATION IRREGULAR	METRORRHAGIA	NIPPLE OEDEMA
NIPPLE PAIN	NIPPLE SWELLING	OESTROGEN DEFICIENCY
OESTROGENS TOTAL URINE DECREASED	OLIGOMENORRHOEA	OSTEOPENIA
OSTEOPOROSIS	PAINFUL EJACULATION	PITUITARY AMENORRHOEA
PREMATURE EJACULATION	PROLACTIN-PRODUCING PITUITARY TUMOUR	PSEUDOGYNAECOMASTIA
SEXUAL DYSFUNCTION	SEXUAL INHIBITION	
BREAST ENLARGEMENT FEMALE	HYPOGONADISM FEMALE	HYPOGONADISM MALE
PRIMARY HYPOGONADISM	SECONDARY HYPOGONADISM	INFERTILITY FEMALE
INFERTILITY MALE	LOSS OF LIBIDO	ORGANIC ERECTILE DYSFUNCTION
PSYCHOGENIC ERECTILE DYSFUNCTION		

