8.2. Subject Exclusion Criteria

The subjects who meet any of the following criteria will be excluded from the study:

- 1. Subject is at high risk of non-compliance in the opinion of the Investigator.
- 2. Subject plans to initiate treatment with a prohibited psychotropic medication during the study.
- 3. Subject plans to initiate treatment with transcranial magnetic stimulation (TMS), electroconvulsive therapy (ECT), vagus nerve stimulation (VNS), or deep brain stimulation (DBS) during the study.
- 4. Subject experienced a moderate or severe hyperprolactinemia-related AESI in the lead-in study of SEP-4199 CR.
- 5. Subject will require treatment with a drug that is associated with increases in QTc interval (see Section 23, Appendix IV for a list of medications, not all inclusive).
- 6. Subject had any of the following at Visit 6/EOT (Day 42) of the lead-in study of SEP-4199 CR based on machine reading:
 - increase in QTcF interval of ≥ 30 msec from Baseline of the lead-in study of SEP-4199 CR AND a QTcF interval ≥ 480 msec
 - increase in QTcF interval \geq 60 msec from Baseline of the lead-in study of SEP-4199 CR
 - QTcF interval > 500 msec
 - treatment-emergent clinically significant ECG abnormality.

- Subject is considered by the Investigator to be at imminent risk of suicide or injury to self or others, has a MADRS item 10 (suicidal ideation) score ≥ 4, or answers "yes" to "suicidal ideation" item 4 (active suicidal ideation with some intent to act, without specific plan) or item 5 (active suicidal ideation with specific plan and intent) on the C-SSRS assessment at Visit 6/EOT (Day 42) of the lead-in study of SEP-4199 CR.
- 8. Female subject of child-bearing potential has a positive urine pregnancy test at Visit 6/EOT (Day 42) of the lead-in study of SEP-4199 CR or plans to become pregnant during the current study.
- 9. Subject tests positive for any drug of abuse or cannabis at Visit 6/EOT (Day 42) of the lead-in study of SEP-4199 CR.

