12.1.3. Adverse Events of Special Interest

Adverse events of special interest (AESI) collected during the study will include all hyperprolactinemia-related events, regardless of seriousness. Hyperprolactinemia-related AESI include, but are not limited to the following:

- Galactorrhea/breast discharge
- Breast disorders including gynecomastia, pain, swelling (moderate or severe events only)
- Lack of or delayed menorrhea, or other menstrual disorders
- Fractures/osteoporosis/osteopenia
- Sexual dysfunction in females and males including erectile dysfunction/changes in libido
- Any estrogen-related laboratory abnormality
- Prolactin-producing pituitary tumor
- Hirsutism

Subjects should be instructed to notify the clinical site within 24 hours if they develop any of the signs or symptoms noted above.

Subjects who develop any of the following AESI: amenorrhea (missed menses for a minimum of 3 months), symptomatic gynecomastia, or galactorrhea that does not resolve within 2 weeks of temporary study drug interruption or that recurs with re-challenge must be discontinued from the study, referred to the Investigator for follow-up evaluation, and followed until the event resolves. Re-challenge will be at the Investigator's discretion (see Section 13.1).

For AESI, if the event meets seriousness criteria, the Investigator will report the event to the Sponsor within 24 hours of the site being made aware of the event, as outlined in Section 12.4.1. AESI that do not meet seriousness criteria will be reported by the Investigator to the Sponsor within 5 business days of site awareness and in the same manner that SAEs are reported.

12.2. **Objective Findings**

Clinically significant changes from signing of the ICF in objective findings (eg, clinical laboratory value, ECG value, vital signs, and physical or neurological examination observation), as determined by the Investigator, will also be recorded as AEs.

When a clear diagnosis is available that explains the objective findings, this diagnosis will be recorded as the AE, and not the abnormal objective finding (eg, viral hepatitis will be recorded as
the AE, not transaminase elevation). If a definite diagnosis is not available, then the sign (eg, clinically significant elevation of transaminase levels) or symptom (eg, abdominal pain) will be recorded as the AE.

Clinical laboratory test results and ECG tracings and over-read reports will be reviewed, signed, and dated by the Investigator.

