## 4.7. CHANGES TO ANALYSIS FROM PROTOCOL

Because of the small sample size due to study early termination, the following main changes will be made for this study:

- Only 2 treatment groups will be formed based on a subject's previous participation in the lead-in study of SEP-4199 CR (SEP-SEP: previously randomized to any SEP-4199 CR dose group and PBO-SEP: previously randomized to placebo).
- No subgroup summaries will be performed.
- No summaries using Follow-up population will be performed.
- Except for PWC, follow-up period summaries will not be performed, PWC will be summarized by Safety population.
- AE will not be summarized by high-level term (HLT).
- No Kaplan-Meier curves will be plotted for time to discontinuation and time to the earliest onsets of the selected AESI. The Kaplan-Meier estimation will also not be performed.
- To be consistent with AIMS and BARS, MSAS will be summarized by total score.

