#### 18.1.1.1. Severity

Severity is classed as mild/ moderate/ severe (increasing severity). AEs with a missing severity will be classified as severe.

If a subject reported an AE more than once within the same SOC/ PT with different severity levels, the

subject will be assigned to a severity level for that SOC/ PT based on the worst case severity (i.e., maximum severity). Event counts will not be included in this summary.

In a separate table, severe AEs will be summarized by SOC and PT.

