#### 18.1.4. ADVERSE EVENTS OF SPECIAL INTEREST (AESI)

A list of preferred terms that are to be combined for assessment of adverse events of special interest (AESI), eg, hyperprolactinemia-related AEs, details of definition are provided in [Appendix 5](#).

AEs potentially associated with the study medication SEP-4199 CR:

- Extrapiramidal symptoms (EPS): SMQ Extrapiramidal symptoms and 4 sub-classes (broad),
- QT prolongation: SMQ Torsade de Pointes/QT prolongation (narrow, broad),

AESI will be summarized by AESI category and preferred term for overall subjects.

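### The SAP's hyperprolactinemia-related AESI query omits the protocol's moderate-or-severe limit on breast disorders, so the tabulated category rate can exceed the protocol-defined rate, and SAP 4.7 does not record the difference

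*SAP*

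**What the plan says.** Protocol 12.1.3 gives an open-ended list of hyperprolactinemia-related AESI. One item has a severity limit: "Breast disorders including gynecomastia, pain, swelling (moderate or severe events only". No other item has one. Galactorrhea and breast discharge form a separate item without a limit.

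SAP 18.1.4 tabulates AESI by category and preferred term and, for the content of the categories, says that "details of definition are provided in" Appendix 5. A5.1 then says that the hyperprolactinemia-related category "is defined as AEs with any of the following preferred terms and all preferred terms that include the word" FRACTURE. Severity is not mentioned.

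The introduction to Appendix 5 describes a comparison before database lock between the query and the AESI tick box in the data capture system, so that the query "can be reconciled for any terms that potentially meet the protocol AESI criteria" but were not ticked, and the reverse. It adds: "Final definition of each customized query will be finalized right before the DBL".

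SAP 4.7 says that, because of the small sample, "the following main changes will be made for this study", and lists seven. They concern treatment groups, subgroups, the follow-up population, follow-up-period summaries and PWC, high-level terms, Kaplan-Meier output and MSAS scoring. None concerns the AESI definition.

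**The concern.** The two documents define the same category differently. A mild case of breast pain, swelling or gynecomastia falls outside the protocol's breast-disorder item but inside the SAP's term list. Appendix 5 itself describes its terms as ones that only potentially meet the protocol criteria, yet no later step tests the severity criterion before the table is produced.

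What is at stake is one reported rate. The primary objective (protocol 5.1, SAP 3.1.1) names AESI among the rates by which long-term safety is judged. The study is descriptive and plans no inference (SAP 7.6), so the tabulated rate is the result. A reader who takes the AESI row to follow protocol 12.1.3 would be reading a broader category without being told.

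**Working it through.** **1. The definitions side by side.**

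| | Protocol 12.1.3 | SAP A5.1 |
|---|---|---|
| Galactorrhea, breast discharge | Any severity | Any severity |
| Other breast disorders, including gynecomastia, pain and swelling | Moderate or severe only | Any severity |

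The mismatch is confined to the second row.

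**2. Terms affected.** Counted from the A5.1 table:

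- Distinct listed preferred terms: 78.
- Terms containing BREAST, NIPPLE or GYNAECOMASTIA: 21.
- Less BREAST DISCHARGE, which has its own unrestricted protocol item: 21 − 1 = 20.
- Less NIPPLE OEDEMA, NIPPLE PAIN and NIPPLE SWELLING, if these are not read as breast disorders: 20 − 3 = 17.

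So 17 to 20 terms are affected, depending on how the protocol item is read for nipple events. The galactorrhoea-type terms are not in this count.

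**3. Which events can reach the table.** Under SAP 18.1, AEs of this study start at or after the first open-label dose. Events that began in the lead-in study and are ongoing at rollover are listed separately and kept out of every AE summary table. Only new-onset mild breast events matter.

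**4. Effect on the rate.** Let N be the Safety Population. Let m be the number of subjects who enter the category only because of a new-onset mild breast event, that is, with no other event that qualifies under the protocol definition. Then

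SAP rate − protocol rate = m / N.

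Because m cannot be negative, the difference is zero or positive. SAP 4.4 gives 64 enrolled. SAP 6.1 requires at least one dose, so N ≤ 64. For m = 1 the difference is at least 1/64 = 1.56 percentage points, about 1.6. For m = 0 there is none. Each subject weighs more in the smaller PBO-SEP or SEP-SEP column, but the documents do not give the split, so no figure is offered there.

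The documents give no rate of mild breast events. The value of m, and hence the actual shift, cannot be computed from them.

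**5. Whether other planned output supplies the protocol-defined count.** SAP 18.1.1.1 tabulates maximum severity by SOC and preferred term. That shows mild breast events term by term. It does not give the number of distinct subjects in the category under the protocol definition, because a subject may have several terms and rows cannot be added. The count would have to be rebuilt from subject-level listings.

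**The case against.** The strongest reply is that A5.1 is a defensible, broader tabulation query. The limit sits in the protocol's section on defining and reporting AESI. The list there is open-ended. The endpoint and analysis text (protocol 6.1 and 15.4.3.1) speaks of hyperprolactinemia-related AEs without a severity condition, and A5.1 uses that label. The broader query also loses no safety information, the breast terms are visible as separate rows, an AESI listing is planned, and with at most 64 subjects a hand count is short. SAP 4.7 claims only to list main changes.

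Part of this stands. The fault is one of definition and disclosure, it runs in the conservative direction, and silence in 4.7 is not evidence of concealment. But an open-ended list adds unlisted events; it does not cancel an express limit on a listed one. Protocol 6.1 and 15.4.3.1 report the incidence of AESI, a category that 12.1.3 defines. SAP 4.7 does find room for changes as small as dropping high-level terms. Appendix 5 leaves the query open until just before lock, but the SAP marked Final shows no filter.

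Two stronger readings are tempting and not supported:

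- **Carried-over mild events.** Protocol 8.2 bars entry only where "Subject experienced a moderate or severe hyperprolactinemia-related AESI in the lead-in study of SEP-4199 CR". A reader might infer that subjects with mild lead-in breast events will swell the AESI table. SAP 18.1 keeps events ongoing at rollover out of the summary tables, and the exclusion criterion says nothing about how often new mild events will arise.
- **A changed primary endpoint.** A reader might infer this from the primary objective. SAP 3.2.1 lists overall AEs, discontinuations due to AEs and SAEs as primary endpoints; AESI incidence is in 3.2.2 among other safety endpoints. None of the three changes.

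**Conclusion.** The point holds as a mismatch between protocol and SAP that the SAP does not disclose. As written, the SAP reports a hyperprolactinemia-related AESI rate that is equal to or higher than the rate under protocol 12.1.3. The difference is at least 1.56 points in ALL EXT for each subject who is in the category solely through a new-onset mild breast event.

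The text comparison and the term count rest on no assumption beyond the reading of the nipple terms (17 or 20). The per-subject figure uses 64 enrolled as the upper bound on the denominator. The number of affected subjects is unknown and may be zero, so it cannot be said that the reported rate will be inflated, only that it can be. The point does not threaten the study's validity. It is worth correcting because a rate named in the primary objective should match its stated definition.

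**What to change.** In SAP 18.1.4 and A5.1, present two counts for the hyperprolactinemia-related category:

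- the count under the protocol definition, with the breast-disorder terms restricted to moderate or severe events;
- the all-severity count that A5.1 now produces.

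State in A5.1 which terms the restriction covers, and in particular whether the three nipple terms are included. Add one line to 4.7 recording that the all-severity query is broader than protocol 12.1.3.

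The cost is one extra table row, one programming condition and two sentences. Severity is already collected for every AE (protocol 12.3), and Appendix 5 already plans to settle the query just before database lock. Showing both counts is better than applying the restriction alone, which would remove mild breast events from the category rate.

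### SAP A5.1 tabulates hyperprolactinemia-related AESI from a closed term list that does not match the protocol 12.1.3 definition, and no rule says how site-flagged events outside the list are counted

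*SAP*

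**What the plan says.** Protocol 12.1.3 covers all "hyperprolactinemia-related events, regardless of seriousness. Hyperprolactinemia-related AESI include, but are not limited to the following", and then gives eight categories. Four matter here:

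- "Sexual dysfunction in females and males including erectile dysfunction/changes in libido"
- "Lack of or delayed menorrhea, or other menstrual disorders"
- "Any estrogen-related laboratory abnormality"
- "Breast disorders including gynecomastia, pain, swelling (moderate or severe events only" is the wording for breast events, and it is the only category with a severity limit.

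SAP 18.1.4 says that the AESI assessment combines preferred terms and refers to Appendix 5 for the definition. A5.1 states that the hyperprolactinemia category "is defined as AEs with any of the following preferred terms and all preferred terms that include the word" FRACTURE. It contains no severity condition.

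The introduction to Appendix 5 describes an AESI tick box in the EDC system, "which allow any event term listed below be ticked, thus would encompass any such event in EDC". It provides for reconciling the box and the query in both directions before database lock, and says the query definition will be finalized just before lock. SAP 4.7, which lists the main changes from the protocol, does not mention the AESI definition.

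**The concern.** The protocol definition is open and, for libido and estrogen, has no direction. The SAP definition is a fixed set of exact terms. An event that a site correctly reports as an AESI under 12.1.3 can carry a preferred term that A5.1 does not list, and the SAP then gives no route into the AESI table.

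AESI rates are one of the four measures in the primary objective (protocol 5.1, SAP 3.1.1). Under the protocol such an event also has consequences during the trial: it must be reported to the sponsor even if non-serious (12.1.3, 12.4), and it bars a dose increase (10.1.1). A subject could be handled as an AESI case throughout and still be missing from the AESI summary.

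**Working it through.** The plan states no AESI count or rate, so there is no figure to reproduce. The check is a comparison of the two definitions, followed by the size of one subject.

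**Term comparison.** A5.1 lists 78 distinct preferred terms, plus every term containing FRACTURE. All eight protocol categories are represented.

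| Protocol 12.1.3 category | A5.1 terms | Not named in A5.1 |
|---|---|---|
| Libido changes, any direction | 3: LIBIDO DECREASED, LOSS OF LIBIDO, and the non-directional LIBIDO DISORDER | Increased libido |
| Estrogen abnormality, any direction | 4: BLOOD OESTROGEN DECREASED, OESTROGEN DEFICIENCY, OESTROGENS TOTAL URINE DECREASED, and the non-directional BLOOD OESTROGEN ABNORMAL | Increased estrogen |
| Menstrual disorders, open | 10: absent, scant, delayed, irregular or intermenstrual bleeding, ANOVULATORY CYCLE, and the generic MENSTRUAL DISORDER | Heavy, frequent or painful menstruation |
| Breast disorders, moderate or severe | 16 terms containing BREAST, 3 containing NIPPLE, 2 of the gynecomastia type, all at any severity | Nothing missing; the list is wider |

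One of the 16 BREAST terms, BREAST DISCHARGE, belongs to a protocol category that has no severity limit. That leaves 15 + 3 + 2 = 20 breast-type terms to which the limit would apply. Only two listed terms contain the word INCREASED: one for blood prolactin and one for a bone-metabolism marker.

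A5.1 also adds terms that 12.1.3 does not name: prolactin laboratory findings, bone-turnover tests, hypogonadism and infertility. The mismatch therefore runs both ways.

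**Do the generic terms catch the rest?** Not by the structure of the list. A5.1 names "LIBIDO DISORDER" and LIBIDO DECREASED as separate entries, and MENSTRUAL DISORDER alongside OLIGOMENORRHOEA and METRORRHAGIA. If a generic entry also captured specific events, the specific entries would be redundant.

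**Size.** SAP 4.4 gives 64 enrolled subjects. If all were dosed, one subject is 1/64 = 1.6 percentage points.

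For illustration only, assume 6 subjects meet the A5.1 list, a tabulated rate of 6/64 = 9.4%. Let x be subjects with a protocol-defined AESI but no listed term, and y be subjects whose only listed term is a mild breast event. The protocol-defined rate is (6 + x − y)/64:

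- x = 1, 2, 3 with y = 0: 7/64 = 10.9%, 8/64 = 12.5%, 9/64 = 14.1%
- x = 0 with y = 1, 2, 3: 5/64 = 7.8%, 4/64 = 6.3%, 3/64 = 4.7%

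The values 6, x and y are assumptions; the documents give no event counts. The range from 4.7% to 14.1% on either side of 9.4% shows only that the sign is open.

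**The case against.** The strongest case on the other side has five parts.

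1. **Every protocol category is represented, with generic terms.** This is correct. A reader who infers that the list holds only decrease terms for libido and estrogen would be wrong. What is missing is narrower than that.
2. **The list is not narrower overall, so an understated AESI rate is not shown.** This also stands. The absent breast severity limit and the added terms work in the other direction.
3. **Omission depends on coding.** The documents do not contain MedDRA, so it cannot be checked here which term a given verbatim would receive. It can be said that some events may be left out, not that they will be. Two tempting further examples are weak for related reasons. Decreased bone density is not named in 12.1.3, and A5.1 has BONE DENSITY ABNORMAL and OSTEOPENIA. Delayed ejaculation might be coded to EJACULATION DISORDER, which is listed. Estrogen is not among the laboratory tests in protocol Appendix II, so an estrogen finding would have to come from testing outside the protocol.
4. **Appendix 5 has two-way reconciliation and allows the query to be finalized before lock.** This is the most relevant safeguard, and it may well bring discordant events to light. It does not say what is done with them: no sentence adds a ticked, unlisted event to the table. The same text says the final query is to be displayed in the SAP before sign-off, and this SAP is marked Final.
5. **The events remain in the overall AE tables and listings, and SAP 3.2.1 does not count AESI among the primary endpoints.** Both are true, and they limit the harm to the AESI summary. AESI rates nevertheless remain part of the primary objective in both documents.

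**Conclusion.** The concern holds in this form: the A5.1 list and protocol 12.1.3 differ in both directions, and the SAP does not say how an event flagged by the site but absent from the list is tabulated. Protocol-defined AESI involving increased libido, increased estrogen, or heavy, frequent or painful menstruation can be left out of the AESI rate, depending on coding and on what reconciliation does. Mild breast events, which the protocol excludes, would be counted.

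The net direction of error cannot be determined from the documents. Each affected subject changes the overall rate by about 1.6 points, assuming all 64 enrolled were dosed. SAP 6 counts as enrolled anyone who signed consent, so the dosed number may be smaller and the step larger. The step is also larger within PBO-SEP or SEP-SEP. The point is worth correcting because the change is small and it aligns a primary-objective measure with its protocol definition.

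**What to change.** In SAP 18.1.4 and A5.1:

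1. Define the tabulated hyperprolactinemia-related AESI as (site AESI tick box = Yes) OR (A5.1 term). State that the tick box follows protocol 12.1.3 and is not confined to the listed terms; otherwise the union adds nothing.
2. Add the missing preferred terms for libido change, estrogen abnormality and menstrual disorder. Check the list against the coding dictionary at the same time: Appendix 5 cites MedDRA 24.1, whereas SAP 18.1 codes AEs in 22.0.
3. Apply the protocol's moderate/severe limit to the breast terms, or declare the departure in SAP 4.7. Without this step the union alone would still count mild breast events through the list.
4. Provide a listing of events for which the tick box and the term list disagree.

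The cost is SAP wording, one more condition in the AESI flag, a severity condition if that option is chosen, and one listing. The downside is that a few menstrual or sexual events, possibly unrelated to prolactin, would be counted; the listing lets a reader see them.
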